5.6 Appendix A: Vital signs notable criteria

| Table 5-3 | Vital Signs Notable Criteria |
|-----------|------------------------------|
|-----------|------------------------------|

| Vital Sign Variable | Notable Criteria |
|---------------------|--|
| Pulse (beats/min) | > 120bpm or Increase of \geq 15 bpm from baseline |
| | or |
| | < 50bpm or Decrease of ≥15 bpm from baseline |
| Systolic BP (mmHg) | >180 mm Hg or Increase of ≥20 mm Hg from baseline |
| | Or |
| | < 90 mm Hg or Decrease of ≥ 20 mm Hg from baseline |
| Diastolic BP (mmHg) | > 105 mmHg or Increase of \geq 15 mm Hg from baseline |
| | Or |

< 50 mmHg or Decrease of ≥ 15 mm Hg from baseline

5.7 Appendix B: Clinically notable laboratory values

Table 5-4 Clinically Notable Laboratory Values

| Notable Values | | | | | | |
|--------------------------------------|--|----------------------------------|------------|--|--|--|
| Laboratory Variable | Gender (M/F/Both) | Gender Standard Units (M/F/Both) | | | | |
| LIVER FUNCTION AND RELATED VARIABLES | | | | | | |
| SGOT (AST) | F | >93 U/L | >93 U/L | | | |
| SGOT (AST) | М | >111 U/L | >111 U/L | | | |
| SGPT (ALT) | F | >90 U/L | >90 U/L | | | |
| SGPT (ALT) | М | >123 U/L | >123 U/L | | | |
| Total bilirubin | Both | >3.6 mg/dL | >63 µmol/L | | | |
| Alkaline Phosphatase | F | >832 U/L | >832 U/L | | | |
| Alkaline Phosphatase | М | >1032 U/L | >1032 U/L | | | |
| | HEMATOLOG | Y VARIABLES | | | | |
| Neutrophils | Neutrophils Both <1.5x 10 ³ /uL <1.5x10 ⁹ /L | | | | | |

Note: Only selected lab parameters which have potential to be sensitive to AMG 334 exposure are listed.

5.8 Appendix C: Criteria for ECG abnormalities

Table 5-5ECG Abnormality Ranges

| ECC Demonster | Abnormality Flags | | | |
|---|--|------------------------------------|--|--|
| ECG Parameter | Absolute | Relative* | | |
| RR Interval | Low: < 600 msec ; High: > 1200 msec | Low: \leq -20%; High: \geq 20% | | |
| PR interval | Low: < 120 msec ; High: > 200 msec | Low: \le -20%; High: \ge 20% | | |
| QRS Interval | Low: < 60 msec ; High: > 109 msec | Low: \leq -20%; High: \geq 20% | | |
| QT Interval | Low: < 320 msec ; High: > 450 msec | Low: \leq -20%; High: \geq 20% | | |
| QTcB Interval (Bazett's correction) | Low: < 320 msec ; High: > 450 msec | Low: \leq -20%; High: \geq 20% | | |
| QTcF Interval (Fridericia's correction) | Low: < 320 msec ; High: > 450 msec | Low: \leq -20%; High: \geq 20% | | |
| *Relative change from | previous measurement in percent (% | | | |

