#### Table 6-1Assessment Schedule

Period	Scree	ning	Treatment			Follow-Up		
Visit Name	Screening	Baseline	Treatment	Week 2 	Week 4	Week 8	End of Treatment	Follow-Up
Visit Numbers 	1	20	110	120	130	140	150 and TD/PSD	1999
Days	-42 to -28	-28 to -1	Day 1	14	28	56	84	168
Weeks	-6 to -4	-4 to -1	1	2	4	8	12	24
Informed consent	Х							
Medical history/current medical conditions	Х	Х						
Demography	Х	Х						
Safety Follow up Call				Х				
Physical Examination	Х	Х	Х		Х			Х
Vital signs and body measurements 	Х	Х	Х		Х	Х	Х	Х
Electrocardiogram (ECG)	Х		Х		Х		Х	
Hematology	Х		Х		Х		Х	Х
Clinical Chemistry	Х		Х		Х		Х	Х
Pregnancy Test (serum)	Х						Х	
Pregnancy test (urine)		Х	Х		Х	Х		Х
Urinalysis	Х							
Urine Drug Screen	Х							
Hepatitis screen ₄	Х							
Anti-AMG 334 antibodies			Х		Х		Х	Х
Columbia-Suicide Severity Rating Scale (C-SSRS)	Х	Х	Х		Х	Х	Х	Х
Beck Depression Inventory-II (BDI-II)	Х							
Randomization			Х					
Study drug administration			Х		Х	Х		
Clinical Outcome Assessment(s)					X 			

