2.7.4.1 ECG data

The ECG measurements from this clinical study will be performed as per standard of care for routine safety monitoring, rather than for purposes of assessment of potential QTc effect.

Subject incidence of abnormal ECG diagnosis (see Table 5-5) will be summarized by treatment group and by visit, for the DBTP.

ECG measurements will be listed by treatment.

However, since these evaluations may not necessarily be performed under the rigorous conditions expected to lead to meaningful evaluation of QTc data, these data are not expected to be useful for meta-analysis with data from other trials.

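### The relative ECG flag in SAP Table 5-5 is taken against the previous measurement, so at Week 12 it compares two on-treatment values and not change from baseline

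*SAP*

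**What the plan says.** SAP Section 5.8, Table 5-5, sets out "Abnormality Flags" in two columns for RR, PR, QRS, QT, QTcB and QTcF. The absolute column gives fixed limits, for example "Low: < 60 msec ; High: > 109 msec" for QRS and "Low: < 320 msec ; High: > 450 msec" for QT and both corrected QT intervals. The relative column uses one threshold throughout: a fall or a rise of at least 20%. The footnote takes that change from the "previous measurement in percent".

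SAP Section 2.7.4.1 makes the table the basis of a planned output: "Subject incidence of abnormal ECG diagnosis (see Table 5-5) will be summarized by treatment group and by visit, for the DBTP". Otherwise ECG values are listed. No summary of ECG change from baseline is specified.

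Protocol Table 6-1 schedules ECGs at Screening, Day 1, Week 4 and End of Treatment (Week 12), with none at Week 8 or at follow-up.

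Elsewhere the SAP uses the pre-treatment value. Section 2.1.1.2 defines baseline for safety data as the last evaluable value before first dosing. The change criteria for vital signs in Table 5-3 (Section 5.6) are relative to baseline, and Section 2.7.4.2 adds a change-from-baseline summary for vital signs.

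**The concern.** A by-visit incidence table of abnormal ECG findings is normally read as showing how many patients in each arm differ from their state before treatment. With the schedule above, the relative flag has that meaning at Week 4, where the preceding scheduled ECG is the Day 1 one. It loses that meaning at Week 12, where the preceding scheduled ECG is Week 4, after dosing has begun. The two visits in the same table then measure different things.

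Three distortions follow at Week 12: a persistent change drops out of the relative count, a slow drift never enters it, and a recovery can enter it as a new abnormality. The SAP gives no reason for treating ECG differently from vital signs, and no other planned ECG summary restores the comparison with baseline.

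**Working it through.** The plan states no figure to reproduce. The check applies the Table 5-5 rule to example values, first with the reference in the footnote and then with baseline.

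**Inputs**
- Relative flag: raised if 100 × (x − reference)/reference is ≤ −20 or ≥ 20 (Table 5-5).
- Absolute limits: RR "Low: < 600 msec ; High: > 1200 msec"; PR "Low: < 120 msec ; High: > 200 msec"; QRS "Low: < 60 msec ; High: > 109 msec"; QT, QTcB and QTcF "Low: < 320 msec ; High: > 450 msec".
- Visits: Day 1, Week 4, Week 12 (Protocol Table 6-1).
- ECG values: assumed for illustration, because the documents contain no ECG data.

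**Results**

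| Pattern | Day 1 / Wk 4 / Wk 12 (ms) | Wk 4 vs Day 1 | Wk 12 vs Wk 4 (SAP rule) | Wk 12 vs Day 1 | Absolute limit crossed |
|---|---|---|---|---|---|
| Sustained | PR 140/175/175 | +25.0% | 0.0% | +25.0% | No |
| Sustained | RR 900/700/700 | −22.2% | 0.0% | −22.2% | No |
| Drift | QRS 80/94/108 | +17.5% | +14.9% | +35.0% | No |
| Drift | PR 150/175/198 | +16.7% | +13.1% | +32.0% | No |
| Recovery | PR 140/178/140 | +27.1% | −21.3% | 0.0% | No |
| Sustained | QTcF 400/485/485 | +21.25% | 0.0% | +21.25% | Yes, Wk 4 and Wk 12 |
| Drift | PR 160/185/215 | +15.6% | +16.2% | +34.4% | Yes, Wk 12 |

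For the first drift row: 94/80 = 1.175, 108/94 = 1.149, 108/80 = 1.35.

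- In the first two rows the patient is flagged at Week 4 and not at Week 12, although nothing has changed between the two visits.
- In the third and fourth rows no flag is raised at either visit.
- In the recovery row the patient is back at the starting value and is flagged at Week 12.
- In the last two rows the absolute flag catches at Week 12 what the relative flag misses.

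**How far the gap can extend.** Two steps each just under 20% can accumulate to almost 1.2 × 1.2 − 1 = +44%, or 0.8 × 0.8 − 1 = −36%, with no relative flag.

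**Where the absolute limits do not help.** A rise of exactly 20% stays within the upper limit when baseline is no higher than that limit divided by 1.2. A fall of exactly 20% stays within the lower limit when baseline is at least that limit divided by 0.8. For baselines that start within the limits:

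| Interval | +20% stays inside for baseline (ms) | −20% stays inside for baseline (ms) |
|---|---|---|
| RR | 600 to 1200/1.2 = 1000 | 600/0.8 = 750 to 1200 |
| PR | 120 to 200/1.2 = 166.7 | 120/0.8 = 150 to 200 |
| QRS | 60 to 109/1.2 = 90.8 | 60/0.8 = 75 to 109 |
| QT, QTcB, QTcF | 320 to 450/1.2 = 375 | 320/0.8 = 400 to 450 |

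From a QTc baseline above 375 ms, a sustained rise of 20% or more always exceeds 450 ms and remains flagged at Week 12.

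**With baseline as the reference**, the first four rows are all flagged at Week 12 and the recovery row is not.

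**The case against.** A reader might infer that a lasting ECG change vanishes from the Week 12 safety table. The documents do not support that. The absolute flags still apply at Week 12. A one-step change of 20% or more is counted at Week 4, so an excess in one arm would show there. Every ECG value is listed, so change from baseline can be recovered by hand. Under Protocol Section 6.5.6, tracings that raise a safety concern are repeated and sent to the central laboratory, and clinically significant abnormalities go on the CRF. These points stand, and they confine the problem to the relative flag for values inside the absolute limits.

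A reader might also infer that the rule leaves the trial's cardiovascular concern unmonitored. Protocol Section 3.6 describes a theoretical reduction in compensatory vasodilation under ischemic conditions and reports no evidence of cardiovascular risk so far. It does not mention conduction intervals. SAP Section 2.7.4.1 calls the ECGs routine monitoring and not an assessment of QTc effect, and Section 2.7 plans no safety testing. This limits the consequence. It does not justify the choice of reference, since a routine by-visit summary also needs a fixed pre-treatment comparator.

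Two further cautions are fair. The drift examples end just inside the limits, so each value is normal on the absolute criteria, and the documents give no basis for saying how often such patterns would occur. Section 2.7.4.1 also does not say whether the incidence counts absolute flags, relative flags or both; that may be settled in the output shells, which are not part of these documents.

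**Conclusion.** The point holds for the relative flag only. At Week 12 that flag measures change between two on-treatment ECGs. Among values inside the absolute limits, it drops sustained changes that were counted at Week 4, misses two-step drift at both visits (up to nearly +44% or −36%), and can mark a return to baseline as abnormal.

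The effect is confined to one descriptive safety table. Efficacy results and type I error are untouched. It is a minor point, worth correcting because the correction is simple.

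The conclusion assumes that ECGs follow the schedule and that the incidence table counts the relative flags. If an unscheduled or repeat ECG falls between visits, the reference moves again, and the SAP does not say which tracing then counts as the previous one. How many patients would be affected cannot be estimated from the documents.

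**What to change.** In the Table 5-5 footnote, define the relative change against the safety baseline of SAP Section 2.1.1.2 at every post-baseline visit, in line with Table 5-3 for vital signs. Change from the previous measurement can be kept as an additional flag in the listing. State in Section 2.7.4.1 whether the incidence table counts absolute flags, relative flags or both.

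The cost is one footnote, one clarifying sentence and a small programming change. The ECGs needed are already on the visit schedule.

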5.9 Appendix D: Patient-reported Outcome Forms/Instruments

When you have headaches, how often is the pain severe? Never Rarely Sometimes Very Often Always How often do headaches limit your ability to do usual daily activities including household work, work, school, or social activities? Never Rarely Sometimes Very Often Always When you have a headache, how often do you wish you could lie down? Rarely Sometimes Very Often Never Always In the past 4 weeks, how often have you felt too tired to do work or daily activities because of your headaches? Never Rarely Sometimes Very Often Always In the past 4 weeks, how often have you felt fed up or irritated because of your headaches? Sometimes Rarely Very Often Never Always In the past 4 weeks, how often did headaches limit your ability to concentrate on work or daily activities? Very Often Rarely Sometimes Never Always COLUMN 1 COLUMN 2 COLUMN 3 COLUMN 4 COLUMN 5 (6 points each) (10 points each) (13 points each) (8 points each) (11 points each)

5.9.2 Headache Impact Test (HIT-6) scoring

Scoring:

Scoring of HIT-6 total score is computed by QualityMetrics software with total score ranging from 36 to 78. HIT-6 scores are categorized into 4 grades, representing little or no impact (49 or less), some impact (50-55), substantial impact (56-59), and severe impact (60-78) due to headache.

5.9.4 Beck Depression Inventory -II (BDI-II) scoring

Beck Depression Inventory - II (BDI-II)

This instrument consists of 21 items, each with 4 or 6 statements regarding symptoms of depression. One statement is selected for each item. Each statement has an associated value. Two of the items' values are recoded for scoring, while the others retain their original value.

| Group | Original value Rescored value | |
|---------------------|-------------------------------|---|
| 1 – 15, 17, 19 - 21 | 0 | 0 |
| | 1 | 1 |
| | 2 | 2 |
| | 3 | 3 |
| 16, 18 | 0 | 0 |
| | 1 | 1 |
| | 2 | 1 |
| | 3 | 2 |
| | 4 | 2 |
| | 5 | 3 |
| | 6 | 3 |

Score

A single score is calculated by adding up the (rescored) values of the 21 items. The range of values is 0-63.

Missing values:

if more than 2 items have missing values, the total BDI score will be missing. If one or two items are missing, their score can be imputed with the mean of the non-missing scores before summing.

Interpretation:

0 – 13: minimal depression

- 14 19: mild depression
- 20-28: moderate depression
- 29-63: severe depression

Missing data:

If more than 2 items have missing values, the total BDI score will be missing. If one or two items are missing, their score can be imputed with the mean of the non-missing scores before summing.

5.10 Appendix E: Geographic regions

Table 5-6Geographic regions

| Geographic region | Country |
|---------------------------------------|--------------|
| India | India |
| Taiwan | Taiwan |
| Korea | Rep of Korea |
| Asia (excluding India, Taiwan, Korea) | Malaysia |
| | Singapore |
| | Thailand |
| | Vietnam |
| | Philippines |
| Other | Lebanon |
| | Argentina |
| | Mexico |

5.11 Appendix F: MMD derivation, exceptions

5.11.1 Assigning Headache and Migraine Days to Events Spanning Midnight

The diagram below shows all of the possible scenarios for time-based determination of assignment of events to days when the events span midnight

Scenario 8: Day 2 only event, regardless of medications taken or not taken or when they are taken

5.11.2 Spanning Midnight Rules for Multi-Day Events Longer Than Two Days

When an event spans two or more full days, with "tail" conditions (event lasts for less than 30 minutes or less on one side of midnight or the other), the "tail" conditions must be checked separately at each end of the event (beginning and end) to determine which days are included in the event expanse. The example below shows an event spanning 3 days. For events spanning more than 3 days, where there are n total days of the event, the endpoints would be Day 1 (Day 1 in the example below), Day n (Day 3 in the example below), and Days 2 to n-1 (Day 2 in the example below).

Example

A headache event starts 28 minutes before midnight (Day 1), extends across a full day (Day 2), and ends 25 minutes after the next midnight (Day 3)

In this example, because the midnight scenario between Day 1 and Day 2 (Scenario 6) determines that Day 1 will NOT be counted as a headache/migraine day, and the midnight scenario between Day 2 and Day 3 (Scenario 2) determines that Day 3 will NOT be counted as a headache/migraine day, the event that started on Day 1 and ended on Day 3 will only count as a headache/migraine day on Day 2.

6 Reference

Headache Classification Committee of the International Headache Society (IHS, 2013), The International Classification of Headache Disorders, 3rd edition (beta version), *Cephalalgia* Vol. 33(9) 629–808.

Koch G. G., Amara I. A., Davis G. W., and Gillings D. B. (1982). A review of some statistical methods for covariance analysis of categorical data, *Biometrics*, 38(3), 553–595.

Koch G. G., Carr G. J., Amara I. A., Stokes M.E., and Uryniak T. J. (1990). Categorical Data Analysis, *In Statistical Methodology in the Pharmaceutical Sciences*, Ed. by Berry DA. New York: Marcel Dekker, 291–475.

Lehmann, E. L. (1975). Nonparametrics: Statistical Methods Based on Ranks, *San Francisco: Holden-Day*, 132-137, 145.

Schafer, J. L. (1997). Analysis of Incomplete Multivariate Data, New York: Chapman and Hall.

Van Elteren, P. H. (1960). On the combination of independent two-sample tests of Wilcoxon, *Bulletin of the International Statistical Institute*, 37, 351-361.
